1 SYNOPSIS

| Title | A Phase 2 Randomized, Double Blinded, Placebo Controlled Study of Oral Camostat Mesilate Compared to Standard Supportive Care in Subjects with Mild-Moderate COVID-19 | | | | | |
|------------|---|--|--|--|--|--|
| Design | This is a Phase 2 Double Blinded, Placebo Controlled Study evaluating the efficacy and safety of oral camostat mesilate in adult subjects with PCR-positive, mild-moderate COVID-19 infections. | | | | | |
| | Subjects will be randomized to receive either camostat mesilate +current Standard of Care (SOC) or SOC + placebo. | | | | | |
| | Study participants will be randomly assigned 1:1 to two tablets of oral camostat mesilate (100 mg/tablet) four times a day plus SOC or SOC plus placebo for 10 days. | | | | | |
| | Subjects in the SOC arm will receive placebo. | | | | | |
| | The total anticipated duration of the study for each patient is 28 days. | | | | | |
| Objectives | Primary Objective To evaluate the efficacy of oral Foipan (camostat mesilate, 200 mg, four times a day for ten days) compared with placebo plus current standard of care in reducing the area under the curve (AUC) through day 10 of viral shedding of SARS-CoV-2 virus in patients with mild-moderate COVID-19. Secondary Objectives 1. To evaluate the efficacy of oral camostat mesilate plus SOC compared with placebo plus current SOC in reducing the AUC up through day 28 of viral shedding of SARS-CoV-2 virus in patients with mild-moderate COVID-19. 2. To evaluate the efficacy of oral camostat mesilate plus SOC compared with placebo plus current SOC in reducing the duration of viral shedding of SARS-CoV-2 virus in patients with mild-moderate COVID-19. 3. To evaluate the efficacy of oral camostat mesilate plus SOC compared with placebo plus SOC in reducing the duration of symptoms, hospitalizations or ED visits, or mortality in patients with mild-moderate COVID-19. 4. To evaluate the proportion of individuals with a negative SARS-CoV2 RT PCR test on days 7, 14 and 28. 5. To assess the safety and tolerability of camostat mesilate in this subject population. 6. To assess the development of antibodies against SARS-CoV-2 7. To determine drug levels at one time point on day 5 using the current dosing scheme. | | | | | |
| Endpoints | Primary Endpoint: | | | | | |

Confidential Page 6 of 42

| | AUC of shedding of SARS-CoV-2 virus calculated using the RT-PCR measures of viral load from self-collected nasal swabs on days 1-10. | | | |

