|---------------------------|---|--|--|--|
| | Secondary Endpoints | | | |
| | AUC of shedding of SARS-CoV-2 virus calculated using the RT-PCR measures of viral load from self-collected nasal swabs on days 1-10, 14, 21, and 28. Time until cessation of shedding of SARS-CoV-2 virus, defined as the time in days from randomization to the first negative RT-PCR result of self-collected nasal swabs that is followed by only negative results (i.e. no later positive results are observed). RT-PCR results from oropharyngeal swabs collected on Days 1, 5, 10 and 28 Clinical worsening of COVID-19 in symptomatic subjects (clinical worsening defined the development of respiratory distress or symptoms that require hospitalization) Adverse events AEs and clinical laboratory tests for systemic safety including hematology and clinical chemistry Mortality Development of antibodies to SARS-CoV-2 Time until resolution of symptoms (resolution of symptoms defined as absence of moderate or severe symptoms for at least 24 hours for those reporting moderate or severe symptoms at baseline). | | | |
| | 9. Drug level on day five, one hour after a dose taken on an empty stomach. | | | |
| Study Sites | Stanford University School of Medicine | | | |
| Planned Enrollment | 120 (60 in the camostat mesilate + SOC group and 60 in the placebo + SOC group) | | | |
| Study Population | Adults with confirmed SARS-CoV-2 who are experiencing mild-moderate symptoms | | | |
| Subject Entry Criteria | Inclusion Criteria (all questions must be answered YES) 1. Adults (18-80) 2. Diagnosis of COVID-19 disease: a. Presence of mild-moderate symptoms without signs of respiratory distress (as defined by SpO2 <=94% on room air, RR >=24, HR >=110), with FDA-cleared molecular diagnostic assay positive for SARS-CoV-2 within 72 hours from initial swab to the time of commencing informed consent: Disease is defined as having at least 2 of the following symptoms that are of moderate or higher severity as scored on the COVID Outpatient Symptom Scale (COSS): i. Fever (>98.7F) | | | |

Confidential Page 7 of 42

| • • | \sim 1 |
|-----|----------|
| 11. | Cough |
| | Cousii |

- iii. Shortness of breath
- iv. Fatigue
- v. Headache
- vi. Body ache
- vii. Joint pain
- viii. Chest pressure
- ix. Abdominal pain
- x. Sore throat
- xi. Nasal congestion
- xii. Chills
- xiii. Feeling hot or feverish
- xiv. Runny nose
- xv. Loss of taste
- xvi. Loss of smell
- xvii. Diarrhea
- xviii. Nausea
- xix. Vomiting
- xx. Rash

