7.1 Day 1 (PRE-DOSE)

- Obtain informed consent.
- Verify eligibility per the inclusion and exclusion criteria. (See Sections 5.1 and 5.2)
 - o Review and record medical history to ensure there are no exclusionary illnesses.
 - Review and record concomitant medications for possible prohibited medications. (See Section 6.7)
 - Record date of onset of symptoms
- If subject is female of child-bearing potential and meets inclusion criteria 5.e, obtain urine pregnancy test and proceed if result is negative.
- Measure and record vital signs (BP, HR, Temp, Resp).

Confidential Page 23 of 42

² If such symptoms are observed, administration should be discontinued.

- Collect and record SPO2 by Finger Sensor
- Perform Physical exam (may be done by the Principal Investigator or their designee)
- Collect oropharyngeal swab for virologic testing by RT-PCR and resistance testing.
- Collect blood samples for:
 - o Antibodies to SARS-CoV-2.
 - o Hematology and clinical chemistry laboratory analyses
 - Biobanking
- Perform subject randomization (via EDC) to establish treatment arm (camostat mesilate + SOC or SOC + placebo).
- Explain in home procedures for the study (self-sampling of nasal swabs, temperature, SPO2, completing the daily questionnaire).
- Provide supplies to research subject and review the calendar of return visits

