9 STATISTICAL METHODS

Complete details of all statistical analyses, including methods for handling missing data, will be included in a formal statistical analysis plan (SAP), to be completed as soon as possible.

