9.2 Sample size justification

Approximately 120 patients will be enrolled.

Assuming 1:1 randomization and the use of a two-sided log rank test at the alpha=0.04999 level of significance for the final analysis, 120 patients (60 per arm) events will provide 80% power to detect an effect size of 0.5 using two-sample t-test. This leaves alpha=0.00001 to check for overwhelming efficacy after 50% of participants have completed 24 hours of follow-up.

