9.8 Primary efficacy analysis

To address our primary objective, the AUC SARS-CoV2 viral RNA levels during follow-up will be estimated using the linear trapezoidal method, and mean AUC levels compared between groups using a linear regression model regressing log(AUC) on treatment arm, site, age, and sex. If more than 3 sites are included to address the objectives, we will employ a mixed effects

Confidential Page 31 of 42

model, with a random effect for site. The test will be performed at the two-sided alpha = 0.05 level of significance.

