The number of hospitalizations, emergency department visits, incidence of respiratory failure, deaths, and proportions of subjects alive, not hospitalized, and free of respiratory failure will be estimated for each arm, with 95% confidence intervals. Respiratory failure is defined as the need for mechanical ventilation, ECMO, non-invasive ventilation, or high-flow oxygen

Our analyses will use multiple imputation methods that assume data are missing at random by including all baseline characteristics, treatment assignment, and reasons for missingness in the imputation model. This approach will be applied to any analysis involving endpoints or key variables where any missing data occurs in order to adhere to the ITT principle. Assumptions regarding missingness will be addressed in sensitivity analyses.

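### Does the multiple-imputation rule put the primary Day 1–10 AUC at risk because it does not say whether single swabs or the whole AUC are imputed?

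*Combined protocol and SAP*

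**What the plan says.** The primary endpoint in the Synopsis is "AUC of shedding of SARS-CoV-2 virus calculated using the RT-PCR measures of viral load from self-collected nasal swabs on days 1-10", so each patient contributes ten daily values. Section 9.8 says that the AUC "will be estimated using the linear trapezoidal method" and that log(AUC) is then regressed on arm, site, age and sex. It has no sentence on missed swabs.

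The only imputation rule stands at the end of Section 9.9. The model is described as "including all baseline characteristics, treatment assignment, and reasons for missingness in the imputation model". Although the section deals with secondary analyses, the scope is general: "This approach will be applied to any analysis involving endpoints or key variables where any missing data occurs". The primary AUC is therefore covered. The same paragraph promises sensitivity analyses on the missingness assumptions.

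Section 9 states that full details, "including methods for handling missing data, will be included in a formal statistical analysis plan (SAP), to be completed as soon as possible". That later text is not part of the document under review.

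Viral measurements are also taken by oropharyngeal swab: before dosing under Section 7.1 ("Collect oropharyngeal swab for virologic testing by RT-PCR and resistance testing") and as a secondary endpoint ("RT-PCR results from oropharyngeal swabs collected on Days 1, 5, 10 and 28").

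**The concern.** The rule speaks of endpoints, and the endpoint is the AUC. Read literally, a patient with any missed swab has a missing endpoint, and the AUC is imputed whole from baseline variables, arm and reason for missingness. Up to nine observed swabs from that patient would then go unused.

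Missed swabs are foreseeable. Patients collect them at home for ten days, and the daily questionnaire in Appendix A asks whether one was taken. The trial also has little power to spare, so any loss of precision would fall on the primary test.

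A smaller oddity is that a reason attached to one missed swab has no value on observed swabs. It cannot serve as a predictor if swabs are imputed singly.

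**Working it through.** **The plan's power.** Section 9.2 claims "80% power to detect an effect size of 0.5 using two-sample t-test" with 60 per arm and two-sided alpha 0.04999. The exact t-test gives 77.5%; the normal approximation gives 78.2%. The figure reproduces narrowly by the second route only.

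**How many patients would be affected.** The documents give no miss rate, so 5% and 10% are assumptions. With Day 1 always present and independent misses:
- any gap on Days 2–10: 1 − 0.95^9 = 37%; 1 − 0.90^9 = 61%
- a gap on Days 2–9, with observed days on both sides: 1 − 0.95^8 = 34%; 1 − 0.90^8 = 57%
- Day 10 itself missing: 5%; 10%

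Most incomplete profiles thus have gaps that a straight line can cross. Only the few without Day 10 need anything more.

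**What each handling costs.** Simulation assumptions: 60 per arm; Day 1 load mean 6, SD 1.5 log10; decline 0.35 log10/day; noise SD 0.7; treatment effect 0.2 log10/day; slope SD 0 or 0.15; undetectable results floored at 1 log10; 20 imputations pooled by Rubin's rules. Oropharyngeal load is assumed quantitative. The entries are the variance of the treatment effect divided by its full-data value. Ranges span the two slope SDs.

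| Handling | Raw-load AUC, 5% | Raw, 10% | log10-load AUC, 5% | log10, 10% |
|---|---|---|---|---|
| Whole AUC imputed; Day 1 nasal and oropharyngeal load as predictors | 1.065–1.079 | 1.192–1.227 | 1.110–1.195 | 1.312–1.543 |
| Whole AUC imputed; oropharyngeal load only | 1.239–1.247 | 1.688–1.709 | 1.225–1.288 | 1.645–1.812 |
| Trapezoid across gaps (missing Day 10 imputed) | 1.002 | 1.004–1.005 | 1.000 | 0.999–1.000 |
| Single swabs imputed from all other swabs | 1.005 | 1.009 | 0.995 | 0.990–0.991 |

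Imputing single swabs from only the variables listed in Section 9.9 plus Day 1 load also costs essentially nothing. For scattered gaps, what matters is that the observed swabs are kept.

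**Translation to power.** Replace n by 60 divided by the ratio in the t-test, using the first row.
- log10-load AUC (simulated effect size about 0.49–0.54, so 0.5 is apt): 60/1.110 = 54.1 gives 73.1%, and 60/1.195 = 50.2 gives 69.9%, at 5% missed. 60/1.312 = 45.7 gives 65.7%, and 60/1.543 = 38.9 gives 58.6%, at 10%.
- Raw-load AUC: the simulated effect size is only 0.14–0.15, so power at 0.5 does not belong with these ratios. At 0.145, power is 12.4% with full data, 11.8–11.9% at 5% and 10.9–11.1% at 10%, a loss of about one point.

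The documents do not say which scale is integrated. Taking log(AUC) suggests raw load, since an AUC of log10 load would be logged twice.

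**Bias.** Under load-dependent dropout after Day 5 (26–35% of patients), whole-AUC imputation with Day 1 nasal and oropharyngeal load gave bias of 0.01–0.19 standard errors and type I error of 4.9–5.5%. Swab-level imputation with the same predictors gave 5.0–6.3%. With all earlier swabs as predictors it gave 4.7–5.3% and bias of at most 0.08 standard errors. The Monte Carlo standard error is 0.6 points. The whole-AUC reading costs precision and shows no material inflation of type I error.

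**Which reading the text favours.** The trapezoid needs no equal spacing. The secondary AUC in the Synopsis uses Days 1–10, 14, 21 and 28, so the plan already draws straight lines over 14 − 10 = 4 days and 21 − 14 = 28 − 21 = 7 days. Crossing one missed day is the same operation. No passage says that a missed swab voids the AUC, and the imputation rule lists what is included without closing the list.

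**The case for a change.** The strongest case for a change is pre-specification. Three permitted methods differ in precision on the primary test, and power is already a little under the stated 80%. Other assumed trajectories give a larger loss: with Day 1 mean 6.5, SD 1.0, and only Day 1 load as predictor, simulated power under whole-AUC imputation was 68% at 5% missed and 48% at 10%, against 83% and 80% with full data. Section 10.2 also applies the final methods at the interim, when half the patients need have only 24 hours of follow-up.

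Some of this stands. The unit of imputation is unstated, and whole-AUC imputation would be a poor choice. But every large figure depends on that choice as well as on assumed miss rates and trajectories, and in the same alternative simulation swab-level imputation kept 83% and 81%. The interim difficulty comes from its timing. Patients with one or two swabs have little to bridge or borrow from, whichever unit is imputed.

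Prescribing one detailed imputation model would bring its own difficulties. Section 7.1 lists only the oropharyngeal swab before dosing, so the Day 1 nasal swab may be post-dose and is itself part of the endpoint. The documents do not say that the oropharyngeal result is quantitative. A normal model for log10 load is strained when many results are undetectable. Reasons recorded per patient, such as withdrawal, can still be predictors. Those tied to a single swab would simply drop out of a swab-level model.

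**Conclusion.** No change to the plan follows. The text leaves a detail open, and Section 9 assigns that detail to the separate SAP. The trapezoid already named handles most gaps, and either sensible completion, bridging or single-swab imputation, changes the variance by about 1% or less.

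The harm belongs to one reading that no passage prescribes and a trial statistician would be unlikely to adopt. There, the variance rises by 7–20% at 5% missed swabs and 19–54% at 10% with Day 1 nasal and oropharyngeal load in the model, and by up to 81% with oropharyngeal load alone. The cost is mainly precision; bias stays within 0.2 standard errors when both loads are used. These sizes rest on assumed miss rates, trajectories and a quantitative oropharyngeal result. The conclusion also assumes that the SAP is finished before unblinding, as is usual.

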9.10 Safety Analysis

Confidential Page 32 of 42

The frequency of adverse events and serious adverse events will be tabulated by type and by treatment arm. AEs will be compared by arm using the Chi-squared test or Fisher's exact test, as appropriate, in the safety analysis set.

The original exact terms in the electronic data capture (EDC) system used by Investigators to identify AEs other than symptoms of COVID-19 will be fully described and coded according to the Medical Dictionary for Regulatory Activities (MedDRA). Treatment-emergent AEs will be defined as those occurring coincident with start of treatment and through 28 days post-treatment. TEAEs will be summarized overall and by treatment group and by MedDRA body organ system and preferred term, severity, relatedness, and seriousness.

An overall summary of TEAEs will be presented by treatment, with subject counts and percentages of subjects with the event. This summary will include subjects with any TEAE, any treatment-related TEAE, any serious TEAE, any treatment-related serious TEAE, TEAEs leading to study infusion discontinuation, treatment-related TEAEs leading to study infusion discontinuation, TEAEs leading to death, and treatment-related TEAEs leading to death. The difference in proportions between treatment groups in each of these categories will be calculated.

Summaries of changes over time in laboratory parameters, as well as counts and percentages of laboratory parameters that are Low, Normal, and High compared to the reference ranges will be presented by treatment at each visit and time point. Shift tables will be presented for laboratory parameters with defined severity grades.

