5 SUBJECT POPULATION

5.1 Inclusion Criteria

All criteria must be confirmed as "YES":

- 1. Adults (18 to 80 years old inclusive)
- 2. Diagnosis of COVID-19 disease:
 - a. Presence of mild-moderate symptoms without signs of respiratory distress (as defined by SpO2 <=94% on room air, RR >=24, HR >=110), with FDA-cleared molecular diagnostic assay positive for SARS-CoV-2 within 72 hours from swab to the time of commencing informed consent. Mild-moderate disease is defined as having at least 20f the following symptoms that are of moderate or higher severity as scored on the COVID Outpatient Symptom Scale (COSS)::
 - i. Fever (>98.7F)
 - ii. Cough
 - iii. Shortness of breath
 - iv. Fatigue
 - v. Headache
 - vi. Body ache
 - vii. Joint pain
 - viii. Chest pressure
 - ix. Abdominal pain
 - x. Sore throat
 - xi. Nasal congestion
 - xii. Chills
 - xiii. Feeling hot or feverish
 - xiv. Runny nose
 - xv. Loss of taste
 - xvi. Loss of smell
 - xvii. Diarrhea
 - xviii. Nausea
 - xix. Vomiting
 - xx. Rash
 - b. The date of onset of the first of the above symptoms will be documented.
- 3. Subject or their legal representative understands the requirements of the study and provides written informed consent prior to undergoing any treatment-related procedures.
- 4. If male, subject must:

Confidential Page 18 of 42

- a. Be sterile (e.g., have had a vasectomy at least 6 months prior to Day 1 dosing), OR,
- b. Agree not to donate sperm during the study and for seven days following the last dose of study medication, AND,
- c. Agree to strictly adhere to the following contraceptive measures during the study and for seven days following the last dose of study medication:
 - i. Abstain from sexual intercourse.
 - ii. Use a condom during sexual intercourse with a female of child-bearing potential. In addition, the female partner must use another form of contraception (e.g. intrauterine device [IUD], diaphragm with spermicide, oral contraceptives, injectable progesterone, or subdermal implants).

5. If female, subject must:

- a. Be unable to bear children (have not had a period for ≥ 12 consecutive months, have had her uterus or ovaries removed, or have had a tubal ligation), OR,
- b. Must ensure that their male partner is incapable of fathering a child (e.g., has had a vasectomy at least 6 months prior to study entry), OR,

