6.8 Other Adverse Reactions

Confidential Page 22 of 42

| Incidence ¹ /Adverse Reaction | 0.1%-0.5% | <0.1% | Unknown |
|---|--|--|--------------|
| Hematologic | | Leukopenia, erythrocytopenia | Eosinophilia |
| Hypersensitivity ² | Rash, pruritus | | |
| Gastrointestinal | Nausea, abdominal discomfort, abdominal fullness, diarrhea | Anorexia, vomiting, dry mouth, heartburn, abdominal pain, constipation | |
| Hepatic | Increased AST (GOT), ALT (GPT), etc. | | |
| Renal | | Increased BUN, increased creatinine | |
| Other | | Edema, hypoglycemia | |

¹ The incidences are calculated by including reports from the drug use surveillance

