8.3.2 Definition of an Adverse Event

The FDA Safety Guidance, referencing 21CFR312.32(a), defines an Adverse Event as follows:

Adverse event means any untoward medical occurrence associated with the use of a drug in humans, whether or not considered drug related.

An adverse event (also referred to as an adverse experience) can be any unfavorable and unintended sign (e.g., an abnormal laboratory finding), symptom, or disease temporally associated with the use of a drug and does not imply any judgment about causality. An adverse event can arise with any use of the drug (e.g., off-label use, use in combination with another drug) and with any route of administration, formulation, or dose, including an overdose.

Confidential Page 26 of 42

Adverse Events are **NOT**:

- Clinical events related to the progression of COVID-19.
- Medical or surgical procedures (e.g., surgery, endoscopy, tooth extraction, transfusion). The condition that leads to the procedure is the AE.
- Situations where an untoward medical occurrence has not occurred (e.g., hospitalization for elective surgery, social and/or convenience admissions).

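### The safety analysis in 9.10 withholds MedDRA coding from COVID-19 symptoms, so drug-caused cases of five listed camostat reactions can be left out of the coded TEAE tables

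*Combined protocol and SAP*

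**What the plan says.** **Coding rule (9.10).** The investigator terms that "identify AEs other than symptoms of COVID-19 will be fully described and coded" using MedDRA. The same paragraph continues: "TEAEs will be summarized overall and by treatment group and by MedDRA body organ system and preferred term, severity, relatedness, and seriousness". An event without a code has no row in those tables.

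**Unrestricted statements (9.10, 9.1, 8.3.3).** The first paragraph of 9.10 says "The frequency of adverse events and serious adverse events will be tabulated by type and by treatment arm", with a chi-squared or Fisher's exact test by arm, and 9.1 repeats it. Neither mentions an exception for COVID-19 symptoms. The TEAE definition rests on timing alone: "Treatment-emergent AEs will be defined as those occurring coincident with start of treatment and through 28 days post-treatment". Section 8.3.3 requires new events and exacerbations after dosing to be recorded.

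**Upstream exclusion (8.3.2).** The list of things that are not adverse events includes "Clinical events related to the progression of COVID-19". No rule is given for telling such events from drug effects.

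**Reaction list (6.8).** Gastrointestinal reactions in the 0.1%-0.5% band are "Nausea, abdominal discomfort, abdominal fullness, diarrhea". Those below 0.1% are "Anorexia, vomiting, dry mouth, heartburn, abdominal pain, constipation". Rash is in the 0.1%-0.5% band under hypersensitivity.

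**Symptom list (5.1, item 2a).** Twenty symptoms define the disease for entry. They include abdominal pain, nausea, vomiting, rash and "xvii. Diarrhea".

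**The concern.** Everyone enrolled has symptomatic COVID-19, so a new case of diarrhea, nausea, vomiting, abdominal pain or rash after dosing can plausibly be put down to the disease. Once it is, 9.10 gives it no MedDRA code.

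Randomisation and placebo exist to settle that question: disease symptoms should be equally frequent in both arms, and an excess on camostat points to the drug. Attribution case by case, before the arms are compared, gives that comparison away. If the same share of events is set aside in each arm, the absolute difference shrinks and camostat looks better tolerated than it is.

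Safety and tolerability is secondary objective 5, and section 2.7 says the results will inform use in people who are exposed but not yet ill. For them, gastrointestinal tolerability matters a good deal.

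**Working it through.** The plan states no figure on this point, so there is none to reproduce. The check has three parts.

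**1. Overlap of the two lists.** Counting AST and ALT as two terms and BUN and creatinine as two, 6.8 lists 3 hematologic + 2 hypersensitivity + 10 gastrointestinal + 2 hepatic + 2 renal + 2 other = 21 reactions. Matching each against the 20 symptoms in 5.1:

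| Band in 6.8 | On the symptom list | Not on it |
|---|---|---|
| 0.1%-0.5% (8 terms) | rash, nausea, diarrhea | pruritus, abdominal discomfort, abdominal fullness, AST, ALT |
| <0.1% (12 terms) | vomiting, abdominal pain | the other 10 |
| Unknown (1 term) | none | eosinophilia |

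So 5 of 21 overlap, including 3 of the 8 in the most frequent band. None of the reactions named in 6.7 (shock or anaphylactoid symptoms, thrombocytopenia, hepatic disorder or jaundice, hyperkalemia) is on the symptom list, although dyspnea, given there as a sign of the first, corresponds to a listed symptom.

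**2. Whether another planned analysis catches these events.**
- *Unrestricted AE tabulation (9.1 and the first paragraph of 9.10).* It counts what was recorded as an AE. Section 8.3.2 may already have removed the event, and 8.3.3 also asks for the diagnosis to be recorded instead of individual symptoms. MedDRA is the only coding system named, so how uncoded events would be grouped by type is unclear.
- *Relatedness (8.3.3).* An event counts as related only if the patient's clinical state cannot explain it. That is hard to satisfy for these five symptoms in this population.
- *Daily symptom scale (COSS, Appendix A2).* It records all five in both arms. Its only planned efficacy use (9.9) is time to resolution in patients with moderate or severe symptoms at baseline, repeated for respiratory symptoms. No analysis compares new or worsened symptoms by arm.
- *Laboratory summaries (9.10).* These are separate and unaffected, but do not measure these symptoms.

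**3. Size, under stated assumptions.** There are 60 patients per arm (Synopsis). Power is that of a two-sided Fisher test at 0.05, summed exactly over the binomial outcomes.

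Assume, for illustration, that a gastrointestinal event has true rates of 5% on placebo and 20% on camostat, and that a fraction *f* of events in each arm is set aside as COVID-19 symptoms. Expected counts are 60 × 0.05 × (1 − *f*) and 60 × 0.20 × (1 − *f*).

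| *f* | Expected, placebo vs camostat | Difference in rates | Power |
|---|---|---|---|
| 0 | 3 vs 12 | 15 points | 63% |
| 25% | 2.25 vs 9 | 11.25 points | 44% |
| 50% | 1.5 vs 6 | 7.5 points | 23% |
| 75% | 0.75 vs 3 | 3.75 points | 4% |

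Observed counts of exactly 3/60 and 12/60 would give p = 0.025; 6/60 and 18/60 would give p = 0.011.

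Now take the incidences in 6.8. At 0.5%, 60 × 0.005 = 0.3 events are expected in an arm, and the chance of at least one is 1 − 0.995^60 = 26%. At 0.1% the figures are 0.06 and 6%. If camostat added 0.5 points to a placebo rate of 5% or 10%, Fisher power would be about 1% or 2% with every event coded. At such rates the coding clause costs almost nothing.

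**The case against.** The best defence is that the clause governs only description and MedDRA coding. The sentences on either side of it are unrestricted: all AEs are tabulated and tested by arm, and TEAEs are defined by timing. An uncoded diarrhea recorded as an AE could still enter that tabulation and the overall summary of patients with any TEAE. The wording can also be read as meaning events attributed to the disease, not every term on the entry list, which 9.10 does not cite. On that reading a new diarrhea judged unrelated to COVID-19 is coded as usual.

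This stands, and it limits the point. A reader might infer that camostat's known toxicity disappears from the safety analysis, or that these events are never counted. The documents do not support either: only 5 of the 21 reactions in 6.8 are exposed, none of those named in 6.7 is, and for the five the loss depends on classification.

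The defence does not remove the conflict. Reading the clause as an attribution rule only confirms that unstandardised judgement decides what is coded, and 8.3.2 applies a similar judgement earlier.

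Two further arguments reduce the urgency. The COSS data are collected anyway, so a table can be added without new data. Section 9 also leaves full detail to a formal SAP still to be completed. That makes the SAP the place to correct the wording; it does not show that it will be corrected.

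**Conclusion.** The concern holds in a limited form. The coding clause in 9.10 conflicts with the first paragraph of that section, with 9.1 and with 8.3.3, and together with 8.3.2 it allows drug-caused nausea, vomiting, diarrhea, abdominal pain and rash to be left out of the coded TEAE tables. No planned by-arm analysis of new or worsened symptoms makes up for it.

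The size cannot be fixed from the documents. The fall in power from 63% to between 44% and 4% rests on assumed rates of 5% and 20% and on equal loss in both arms. With the incidences in 6.8 the effect would be negligible, but those include drug-use surveillance for the Japanese product and may not carry over to this regimen and population. The p-values above likewise show what could be hidden; they do not forecast it.

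Severity is moderate. A secondary objective is affected, the primary analysis is not, and the remedy is cheap if it is written down before unblinding.

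**What to change.** 1. In 9.10, remove the restriction on COVID-19 symptoms and code every recorded AE in MedDRA.
2. Reconcile 8.3.2, 8.3.3 and 9.10, so that one rule says when a new or worsened symptom after dosing is recorded, coded and counted as treatment-emergent, identically in both arms.
3. Add one table by arm, with differences in proportions, of the five overlapping symptoms from the daily COSS. Count a symptom if it is new or at least one grade worse than the pre-dose Day 1 value. For rash, which COSS records as yes or no with descriptors, count new onset. State that the Day 1 reference is completed before the first dose.

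The cost is a change of wording and one table from data already collected. The drawback is longer AE tables that contain disease symptoms in both arms.
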